#### **5.4. Withdrawal/Dropout Criteria**

If subjects meet one of the following criteria, study treatment should be permanently discontinued and subjects will be withdrawn from the study. The withdrawal reason should be recorded.

- Hgb <7.5 g/dL  
Note: HemoCue Hgb values will be employed. If an initial Hgb value meets the Hgb stopping criteria, measurement will be repeated at the same study visit (using the same sample) to calculate the average. If the average meets the Hgb stopping criteria, study treatment will be discontinued.
- Subject needs for maintenance dialysis or changes dialysis modality (PD subjects only) during the study period.
- Kidney transplant
- Subject becomes pregnant or intends to become pregnant during the study.
- Diagnosis of new or recurrent cancer

- Liver chemistry abnormalities exceeding the threshold criteria (see Section 5.4.1.)
- Need for chronic (more than 14 days) use of prohibited medication (strong inhibitors/ inducers of CYP2C8 meet this criteria)
- When the investigator (or subinvestigator) considers necessary to withdraw the subject from the study for other reasons

Subjects who meet any of the withdrawal criteria or are withdrawn for other reasons during the treatment phase should be assessed at withdrawal visit after study treatment is discontinued, and will then enter the follow-up phase.

Should a subject fail to attend a required study visit, the investigator (or subinvestigator) should take the following measures:

[figure not shown]
- The investigator (or subinvestigator) or designee should attempt to contact the subject and reschedule the missed visit as soon as possible.
- The investigator (or subinvestigator) should counsel the subject on the importance of maintaining the assigned visit schedule and determine whether the subject is willing to continue his/her participation in the study and/or whether the subject should remain in the study.
- The investigator (or subinvestigator) or designee should make every effort to regain contact with a subject who is deemed “Lost to Follow-up”. All efforts to contact the subject should be documented in the subject’s clinical charts.
- Should the subject continue to be unreachable, then and only then will he/she be considered “Lost to Follow-up.”

A subject may withdraw from the study at any time at his/her own request. The investigator (or subinvestigator) may withdraw a subject from the study at any time for safety or compliance reasons or study conduct considerations. If a subject withdraws from the study, he/she may request destruction of any clinical samples taken, and the investigator (or subinvestigator) must document this in the site study records.

[figure not shown]
#### **5.4.1. Liver Chemistry Stopping Criteria**

**Liver chemistry stopping and increased monitoring criteria** have been designed to assure subject safety and evaluate liver event etiology (in alignment with the FDA premarketing clinical liver safety guidance).

## Liver Chemistry Stopping and Increased Monitoring Algorithm

### Liver Chemistry Increased Monitoring Algorithm with Continued Therapy for ALT $\geq 3$ xULN but < 8xULN

Liver Safety Required Actions and Follow up Assessments Section can be found in Section 12.5. Appendix 5

#### 5.4.1.1. Study Treatment Restart or Rechallenge

Study treatment restart or rechallenge after liver chemistry stopping criteria are met by any subject participating in this study is not allowed.

#### 5.5. Subject and Study Completion

A completed subject is one who has completed all periods of the study including the follow-up visit. The study will be completed with the last subject's last study visit.

### 6. STUDY TREATMENTS

#### 6.1. Investigational Product and Other Study Treatment

The term 'study treatment' is used throughout the protocol to describe any products received by the subject as per the protocol design. Accordingly, 'study treatment' sometimes refers to each product and sometimes refers to multiple products.

#### GSK1278863 (study drug)

The study drug GSK1278863 will be supplied as fast-release film coated tablets for oral administration containing 1 mg, 2 mg, 4 mg, or 6 mg of GSK1278863 (Table 3). There are two sizes of GSK1278863 tablets.

**Table 3 Description of GSK1278863 Tablets**

GSK1278863 tablets of specific content	Description
1 mg tablets, 2 mg tablets, 4 mg tablets	7.0 mm round, standard biconvex, white film coated tablets containing 1 mg, 2 mg, or 4 mg of GSK1278863 as active ingredient
6 mg tablets	9.0 mm round, standard biconvex, white film coated tablets containing 6 mg of GSK1278863 as active ingredient

GSK1278863 tablets of specific content are packed in high density polyethylene (HDPE) bottles, with 35 tablets per bottle. Subjects are to take one to four tablets (Table 4) with water once daily according to the dose level indicated at each study visit. Subjects can take GSK1278863 tablets without regard to food or peritoneal dialysis. The administration schedule (starting dose and dose adjustment) described in Section 6.4.1. should be followed.

**Table 4 Dose Levels of GSK1278863 and Number of Tablets Taken**

Dose level of GSK1278863 (once daily)	1 mg	2 mg	4 mg	6 mg	8 mg	12 mg	18 mg	24 mg
Number of GSK1278863 tablets taken	1 mg tablet ×1	2 mg tablet ×1	4 mg tablet ×1	6 mg tablet ×1	4 mg tablet ×2	6 mg tablet ×2	6 mg tablet ×3	6 mg tablet ×4

Subjects should be instructed to bring GSK1278863 tablets with bottles at each study visit, and all unused GSK1278863 tablets will be collected from subjects at each study visit.

### **Epoetin beta pegol (control)**

The control epoetin beta pegol (brand name: Mircera® Pre-filled Syringe) will be supplied by GSK. This product is an injectable formulation containing 25 µg, 50 µg, 75 µg, 100 µg, 150 µg, 200 µg, or 250 µg of epoetin beta pegol per syringe (0.3 mL) and is supplied as a glass syringe prefilled with epoetin beta pegol solution (clear colorless to pale yellow). Subjects are to receive epoetin beta pegol subcutaneously once every 2 or 4 weeks at the site (Table 5). The administration schedule (starting dose and dose adjustment) described in Section 6.4.2. should be followed.

**Table 5 Dose Levels of Epoetin Beta Pegol and Number of Subcutaneous Doses**

Dose level of epoetin beta pegol (once every 2 or 4 weeks)	25 µg	50 µg	75 µg	100 µg	150 µg	200 µg	250 µg
Number of subcutaneous doses of epoetin beta pegol	25 µg injection ×1	50 µg injection ×1	75 µg injection ×1	100 µg injection ×1	150 µg injection ×1	200 µg injection ×1	250 µg injection ×1

### **6.2. Medical Devices**

The Epoetin beta pegol (Brand name :MIRCERA® Injection Syringe) marketed with the device (kit formulation which was filled liquid medication in glass syringe ) provided for use in this study.

Instructions for medical device are described in the Prescribing Infomration of MIRCERA® Injection Syringe.

The medical device incidents, including those resulting from malfunctions of the device, must be detected, documented, and reported by the investigator throughout the study – see Section 7.4.4.

### **6.3. Treatment Assignment**

The randomization schedule will be generated by GlaxoSmithKline (GSK) using the randomization system (Randall).

In Cohort 1 and Cohort 3 (ND subjects), subjects will be stratified by the current ESA therapy (ESA non-user or ESA user) and the Hgb level on Day 1 and randomized in a 1:1 ratio to one of the two treatment groups according to the randomization schedule. Randomization should precede the study treatment.

- GSK1278863 group
- Epoetin beta pegol group

In Cohort 2 (PD subjects), all eligible subjects will start treatment with GSK1278863 on Day 1.

Subjects will be assigned a randomization number by the Interactive Web Recognition System (IWRS). Once a randomization number has been assigned, it must not be re-assigned. Further details are provided in the Study Reference Manual (SRM).

#### **6.4. Administration Schedule (Starting Dose, Dose Adjustment, and Dosing Frequency)**

##### **6.4.1. GSK1278863 (ND and PD Subjects)**

###### **6.4.1.1. Starting Dose**

For ND subjects randomized to GSK1278863 group

(Cohort 1)

Both ESA non-users and users will start oral treatment with GSK1278863 at the starting dose of 4 mg once daily (Day 1) and remain on the same regimen until the day of Week 4.

(Cohort 3)

- ESA non-users
  - Baseline Hgb  $\geq$ 8.0 g/dL and  $<$ 9.0 g/dL: the subjects will start oral treatment with GSK1278863 at the starting dose of 4 mg once daily (Day 1) and remain on the same regimen until the day of Week 4\*.
  - Baseline Hgb  $\geq$ 9.0 g/dL and  $<$ 11.0 g/dL: the subjects will start oral treatment with GSK1278863 at the starting dose of 2 mg once daily (Day 1) and remain on the same regimen until the day of Week 4\*.
- ESA users will start oral treatment with GSK1278863 at the starting dose of 4 mg once daily (Day 1) and remain on the same regimen until the day of Week 4\*.

\*: The HemoCue Hgb value will be measured for safety confirmation at Week 2 in ND subjects.

When Hgb  $>$  1.0 g/dL increase over 2 weeks, the dose of GSK1278863 is decreased to the next lower dose.

For PD subjects randomized to the GSK1278863 group (Cohort 2)

- ESA non-users will start oral treatment with GSK1278863 at the starting dose of 4 mg once daily (Day 1) and remain on the same regimen until the day of Week 4.
- ESA users will start oral treatment with GSK1278863 at the starting dose of 4 mg once daily (Day 1) and remain on the same regimen until the day of Week 4.

ESA users should skip ESA on Day 1 when treatment with GSK1278863 is started.

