## Study Design

This is a Phase III, open-label, active-controlled, parallel-group, multi-center study to compare the efficacy (demonstration of non-inferiority) and safety of GSK1278863 administered for 52 weeks versus epoetin beta pegol in approximately 286 Japanese ND subjects with renal anemia. This study also includes an open-label, uncontrolled part to evaluate the efficacy and safety of GSK1278863 in approximately 50 Japanese PD subjects. Cohort 1 (ND subjects) and Cohort 2 (PD subjects) were set for target population of this study when the study was planned. Cohort 3 is newly added in Protocol amendment (Amendment No.3). ND subjects will be randomized not to Cohort 1 but to Cohort 3 after Protocol amendment No.3.

Patient population	Cohort	Treatment group	Target number of subjects (randomized)	
ND patient	Cohort 1 	GSK1278863 group (starting dose: 4 mg)	169 subjects 	
		Epoetin beta pegol group		
	Cohort 3 	GSK1278863 group (starting dose: 2 mg or 4 mg  )	117 subjects	286 subjects 
		Epoetin beta pegol group		
PD patient	Cohort 2	GSK1278863 group (starting dose: 4 mg)	50 subjects	

1) At least 50 ESA users and at least 50 ESA non-users will be randomized to Cohort 1.

2) ND patients will be randomized to Cohort 3 and at least 80 ESA non-user will be randomized after Protocol Amendment No.3.

3) GSK 1278863 starting dose in Cohort 3 as below

- ESA non-user (baseline Hgb 8.0-<9.0 g/dL):4 mg
- ESA non-user (baseline Hgb 9.0-<11.0 g/dL):2 mg
- ESA user: 4 mg

4) The exact number of ND subjects randomized to Cohort 1

5) Subjects will be randomized in a 1:1 ratio to one of the two treatment groups

[figure not shown]
ESA: erythropoiesis-stimulating agent

For the patient populations in either cohort, the Hgb criteria are specified according to the presence or absence of prior ESA: ESA non-users with an Hgb level of  $\geq 8.0$  to  $<11.0$  g/dL and ESA users with an Hgb level of 9.0 to 13.0 g/dL will be included in the study.

In Cohort 1 and Cohort 3, eligible ND subjects [total of 286 subjects (169 subjects in Cohort 1, 117 subjects in Cohort 3)] will be stratified by the current ESA therapy and baseline Hgb (ESA non-users:  $\leq 9.5$  g/dL,  $>9.5$  g/dL, ESA users:  $<11.0$  g/dL,  $\geq 11.0$  g/dL) and then randomized in a 1:1 ratio to GSK1278863 or epoetin beta pegol group.

In Cohort 2, 50 eligible PD subjects will be included in the GSK1278863 group.

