#### Starting dose

Simulation results using the longitudinal model in ND subjects as well as the results from clinical studies indicated that GSK1278863 given at a dose of 4 mg may slowly increase Hgb (0.5-1.0 g/dL on average) without a rapid increase greater than 2 g/dL after 4 weeks of treatment in ESA non-users. 4 mg GSK1278863 may also maintain Hgb without a rapid increase greater than 2 g/dL for 4 weeks after switching from prior ESA in ESA users. Therefore, 4 mg was set as starting dose of GSK1278863 when study was planned.

As of Dec 2016 during this study, from the result of a review of blinded data, it was determined that the percentage of ND, ESA-non-user subjects with an Hgb increases of >2.0 g/dL from baseline to Week 4 was higher than expectation described above. This finding was not observed in ND, ESA-user subjects and PD subjects.

Therefore, in the protocol amendment No.3,

- For ND, ESA non-user subjects with baseline Hgb  $\geq 9.0$  g/dL and  $< 11.0$  g/dL, the starting dose of GSK1278863 is changed from 4 mg to 2 mg.
- For ND, ESA non-user subjects with baseline Hgb  $\geq 8.0$  g/dL and  $< 9.0$  g/dL, the starting dose remains at 4 mg.

For ND, ESA-user subjects and PD subjects, the starting dose of GSK1278863 were not changed and remains at 4 mg respectively.

In addition, Week 2 visit for additional Hgb monitoring in Cohort 3 was also included to allow earlier safety assessment of Hgb change at early phase of GSK1278863 treatment. (Refer to Section 6.4.1.)

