###### **6.4.1.2. Maintenance Dose**

From Weeks 4 to 52, interruption of treatment or dose adjustments will be made within the maintenance dose range of 1-24 mg (Table 6) according to the dose adjustment algorithm (Table 7) to achieve and/or maintain Hgb within the target range (11.0-13.0 g/dL) based on the HemoCue Hgb value measured every 4 weeks. Dose changes will be made every 4 weeks. If any of the one-step dose reduction criteria is met during treatment at the minimum maintenance dose (1 mg), treatment should be interrupted; once the one-step dose increase criteria are met, treatment at 1 mg will be resumed. If the one-step dose increase criterion is met during treatment at the maximum maintenance dose (24 mg), treatment at 24 mg should be continued.

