**Table 7 Dose Adjustment Algorithm (GSK1278863)**

Hgb (g/dL)	Hgb increase over 4 weeks (g/dL)	Treatment
>13.0	NA	Interrupt treatment until Hgb decreases to less than 12.5 g/dL Resume treatment at the one lower dose level (If interrupted at 1 mg: resume treatment at 1 mg once the one-step dose increase criteria are met)
12.5-13.0	NA	One-step dose reduction
11.5-12.5	>2.0 	One-step dose reduction
	≤2.0	Continue treatment at the current dose level
7.5-11.5	>2.0 	One-step dose reduction
	0.5-2.0	Continue treatment at the current dose level
	<0.5	One-step dose increase
<7.5	NA	Discontinue treatment permanently  and initiate another appropriate treatment

1) Cohort 3 only: At Week 4, if an Hgb increase of >1.0 g/dL over 2 weeks is observed, the dose of GSK1278863 will be reduced by one step; if an Hgb increase of ≤1.0 g/dL over 2 weeks is observed, treatment will be continued as specified in the dose adjustment algorithm other than one-step dose reduction for an Hgb increase of >2.0 g/dL over 4 weeks.

2): If an initial Hgb value is less than 7.5 g/dL, measurement will be repeated at the same study visit (using the same sample) to calculate the average. If the average meets the Hgb stopping criteria, study treatment will be permanently discontinued.

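### Cohort 3's Week 2 haemoglobin check has no GSK1278863 interruption for a reading above 13.0 g/dL, so by rule an ESA user can be dosed above that level until Week 4

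*Protocol*

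**What the plan says.** Section 6.4.1.1 starts Cohort 3 ESA users on 4 mg once daily and keeps that dose until Week 4, subject to a starred note: "The HemoCue Hgb value will be measured for safety confirmation at Week 2 in ND subjects". If the two-week rise exceeds 1.0 g/dL, "the dose of GSK1278863 is decreased to the next lower dose". No threshold on the Hgb level itself is given on the high side.

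The level-based rule comes later. Section 6.4.1.2 begins: "From Weeks 4 to 52, interruption of treatment or dose adjustments will be made". Table 7 then says, for Hgb above 13.0 g/dL: "Interrupt treatment until Hgb decreases to less than 12.5 g/dL", with resumption one dose level lower. That row shows NA for the four-week increase, so it applies whatever the rate of rise. The Cohort 3 footnote to Table 7 is tied to Week 4.

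On entry, the synopsis says: "ESA users with an Hgb level of 9.0 to 13.0 g/dL will be included in the study". Section 5.1 confirms that 13.0 is inclusive.

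Section 4.5 gives the purpose of the visit: "Week 2 visit for additional Hgb monitoring in Cohort 3 was also included to allow earlier safety assessment of Hgb change". It followed rapid rises in ESA non-users. Of those rises the protocol says: "This finding was not observed in ND, ESA-user subjects and PD subjects".

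**The concern.** The Week 2 value is taken for safety, yet the written rule does not respond to the level at which the protocol stops the drug from Week 4 on. Section 4.5 describes 13.0 g/dL as the interruption point for ESAs. Appendix 2 (Section 12.2) lists interruption based on achieved Hgb, under Section 6.4.1, as a mitigation for excessive erythropoiesis. At Week 2, Section 6.4.1 contains no such interruption.

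The rise-based trigger suits ESA non-users, who enter well below 13.0. It was extended to ESA users, whose entry ceiling equals the interruption level. Control-arm ESA users are injected every four weeks, so they get no further dose between the Week 2 reading and Week 4. On the daily oral drug, dosing continues after the reading has been seen.

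At stake is a short period of dosing above the protocol's own interruption level in very few subjects.

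**Working it through.** **Which readings fall through the rule.** Inputs: entry 9.0 to 13.0 g/dL for users and 8.0 to below 11.0 for non-users (Section 5.1); step-down if the rise exceeds 1.0 (6.4.1.1); interruption above 13.0 from Week 4 (6.4.1.2, Table 7). Readings are in 0.1 g/dL steps.

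- No action despite a reading above 13.0 needs entry + rise ≥ 13.1 with rise ≤ 1.0, so entry ≥ 12.1. The affected entry range is 12.1 to 13.0 and the Week 2 reading can be 13.1 to 14.0. Example: 12.8 to 13.7 is a rise of 0.9, so 4 mg continues.
- Stepped down but still dosed needs a rise above 1.0 that ends above 13.0. Example: 12.5 to 13.6 is a rise of 1.1, so 2 mg continues.
- Either reading at Week 4 would mean interruption.
- Non-users enter at 10.9 at most, so passing 13.0 needs 13.1 − 10.9 = 2.2 g/dL in two weeks, and the step-down always fires. The gap with no action at all is specific to ESA users.

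**How many subjects.** Cohort 3 has 117 subjects with at least 80 non-users (Section 4.1, Table 1): 117 − 80 = 37 users at most. At 1:1, 37 / 2 = 18.5, so about 18 are on GSK1278863.

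The protocol gives no entry distribution and no two-week SD. The assumptions are:

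- mean two-week change 0, in line with Section 4.5's expectation that 4 mg "may also maintain Hgb without a rapid increase greater than 2 g/dL for 4 weeks after switching from prior ESA" in ESA users;
- SD of the change 0.4, 0.6 or 0.8 g/dL, normal, rounded to 0.1;
- entry Hgb either uniform over 9.0 to 13.0, or normal with mean 11 and SD 1 truncated to that range.

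Expected number above 13.0 = 18 × P(entry + change > 13.0). The no-action part adds the condition change ≤ 1.0.

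| Entry Hgb | SD | No action | All above 13.0 |
|---|---|---|---|
| Uniform | 0.4 | 0.68 | 0.70 |
| Uniform | 0.6 | 0.82 | 1.05 |
| Uniform | 0.8 | 0.81 | 1.40 |
| Truncated normal | 0.4 | 0.23 | 0.25 |
| Truncated normal | 0.6 | 0.32 | 0.47 |
| Truncated normal | 0.8 | 0.32 | 0.78 |

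The difference between the last two columns is the group stepped down but still dosed. With 10 users on drug and uniform entry, the totals are 0.39, 0.58 and 0.78. Under uniform entry, 77% to 89% of the no-action readings are only 13.1 to 13.5.

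**For how long.** Week 2 to Week 4 is 14 days. With ±3-day windows at both visits (Section 7.1), the range is (28 − 3) − (14 + 3) = 8 to (28 + 3) − (14 − 3) = 20 days.

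**The case against.** The best defence is that the rule is coherent for its purpose. The visit was added to catch rapid change, and the trigger is a rate. The control arm's Week 2 triggers are also rate-only (Sections 6.4.2.1 and 6.4.2.2). Table 7's level-based rows are maintenance rules: a user entering at 12.5 to 13.0 starts on the full 4 mg, although Table 7 would reduce the dose at that level. Cohorts 1 and 2 have no Week 2 Hgb check, so Cohort 3 is already the stricter. This stands, and a reader who inferred that 6.4.1.1 contradicts Table 7 would be wrong, because Table 7 formally begins at Week 4.

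A reader might also infer that nothing but the step-down can follow a Week 2 reading. The protocol does not support that. Section 5.4 requires permanent discontinuation when HemoCue Hgb is below 7.5 g/dL and lets the investigator withdraw a subject for safety. Section 7 excepts immediate safety concerns from its bar on waivers. However, the first concerns low values, and the other two are discretionary and provide no way to hold and resume treatment.

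The absence of a signal in ESA users does not close the gap. That observation concerned rises above 2.0 g/dL by Week 4, whereas the no-action case needs a rise of only 0.1 to 1.0.

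Finally, uniform entry probably puts too many subjects near 13.0, since users are on continuing ESA therapy and must be at or below 13.0 at both screening and Day 1. That is fair, and it is why the lower set of counts is shown.

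**Conclusion.** The point holds as a minor safety gap that is cheap to close. By the written rule, a Cohort 3 ESA user seen above 13.0 g/dL at Week 2 stays on GSK1278863 until Week 4. The expected number is roughly 0.25 to 1.4 subjects (about 0.2 to 0.8 with no action), each for about two weeks. That range rests on the assumed entry distribution, zero mean change and SD, none of which the protocol gives. The routes by which a reading falls through rest on the text alone.

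Exposure is bounded: the dose cannot rise before Week 4, and a reading still above 13.0 then is interrupted. It might be inferred that the non-inferiority comparison is at risk. It is not, because the endpoint is measured at Weeks 40 to 52, long after the affected fortnight.

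**What to change.** Add to Section 6.4.1.1:

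> Cohort 3: if the Week 2 HemoCue Hgb is >13.0 g/dL, interrupt GSK1278863 as in the >13.0 row of Table 7; this takes precedence over the one-step reduction; recheck at Week 4 and resume one dose level lower once Hgb is <12.5 g/dL.

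The other Table 7 rows need not apply at Week 2. HemoCue measurement and dispensing are already scheduled at that visit (Table 14).

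Costs:

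- A protocol amendment with ethics review, and a small update to the IWRS and dosing guide.
- About one early interruption or fewer. It may not be short: if the Week 4 value is 12.5 or above, the next scheduled reading is Week 8, so the subject could be off drug for 8 − 2 = 6 weeks, having just stopped the prior ESA. Allowing an unscheduled HemoCue check would limit this.
- These subjects' Week 4 Hgb change (Section 3) is altered, as it already is by the step-down, so they should be flagged in that summary.
- The Section 9.4.1 sensitivity analysis that excludes Cohort 3 ESA users reduced at Week 2 should also exclude those interrupted then.
- Early dosing of Cohort 3 ESA users departs slightly further from that of the Cohort 1 ESA users pooled with them in the primary analysis.

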###### **6.4.1.2. Maintenance Dose**

From Weeks 4 to 52, interruption of treatment or dose adjustments will be made within the maintenance dose range of 1-24 mg (Table 6) according to the dose adjustment algorithm (Table 7) to achieve and/or maintain Hgb within the target range (11.0-13.0 g/dL) based on the HemoCue Hgb value measured every 4 weeks. Dose changes will be made every 4 weeks. If any of the one-step dose reduction criteria is met during treatment at the minimum maintenance dose (1 mg), treatment should be interrupted; once the one-step dose increase criteria are met, treatment at 1 mg will be resumed. If the one-step dose increase criterion is met during treatment at the maximum maintenance dose (24 mg), treatment at 24 mg should be continued.

